#### **9.4.3 Analysis of the Secondary Endpoint(s)**

The outcome measures for the correlative studies will be the VT and the results of the clinical rating scales.

#### **9.4.4 Safety Analyses**

None.

#### **9.4.5 Baseline Descriptive Statistics**

Demographic variables, such as age and weight, will be summarized as mean +/- SD.

#### **9.4.6 Sub-Group Analyses**

The sample will be analyzed by sex and age, but is too small to be analyzed by other demographic characteristics.

#### **9.4.7 Tabulation of individual Participant Data**

Individual participant data will be listed by measure and timepoint.

#### **9.4.8 Exploratory Analyses**

None.

### **10 REGULATORY AND OPERATIONAL CONSIDERATIONS**

#### **10.1 Informed Consent Process**

##### **10.1.1 Consent/Assent Procedures and Documentation**

Only the study investigators designated to obtain consent will be allowed to do so. All study investigators obtaining informed consent must have completed the NIMH HSPU training “Elements of Successful Informed Consent”. When consent is conducted for subjects with MDD, HSPU must be present.

The informed consent document will be provided as a physical or electronic document to the participant or consent designee as applicable for review prior to consenting. A designated study investigator will carefully explain the procedures and tests involved in this study, and the associated risks, discomfort and benefits. In order to minimize potential coercion, as much time as is needed to review the document will be given, including an opportunity to discuss it with friends, family members and/or other advisors, and to ask questions of any designated study investigator. A signed informed consent document will be obtained prior to any research activities taking place.

The initial consent process as well as re-consent, when required, may take place in person or remotely (e.g., via telephone or other NIH approved remote platforms used in compliance

with policy, including HRPP Policy 303) per discretion of the designated study investigator and with the agreement of the participant/consent designee(s). Whether in person or remote, the privacy of the subject will be maintained. Consenting investigators (and participant when in person) will be located in a private area (e.g., clinic consult room). When consent is conducted remotely, the participant will be informed of the private nature of the discussion and will be encouraged to relocate to a more private setting if needed. If the consent process is occurring remotely, participants and investigators will view individual copies of the approved consent document on screens at their respective locations; the same screen may be used when both the investigator and the participant are co-located but this is not required.

Note: When required, the witness signature will be obtained similarly as described for the investigator and participant below.

When a hand signature on an electronic document is used for the documentation of consent, this study will use the following electronic platform to obtain the required signatures:

- iMedConsent platform (which is 21 CFR Part 11 compliant)

Both the investigator and the participant will sign the electronic document using a finger, stylus or mouse. Electronic signatures (i.e., the “signature” and a timestamp are digitally generated) will not be used.

The consent process will be documented in CRIS. A copy of the consent form will be given to the participant and also uploaded in CRIS.

#### **10.1.2 Consent for minors when they reach the age of majority**

Minors will not be enrolled in the study.

#### **10.1.3 Considerations for Consent of NIH staff, or family members of study team members**

Consent for NIH employees will be obtained as described in Section 5.3. 2

#### **10.1.4 Consent of Subjects who are, or become, decisionally impaired**

Adults unable to give consent are excluded from enrolling in the protocol. For those subjects that become incapacitated, they will be removed from the study.

### **10.2 Study Discontinuation and Closure**

This study may be temporarily suspended or prematurely terminated if there is sufficient reasonable cause. If the study is prematurely terminated or suspended, the PI will promptly inform study participants, the IRB, and the sponsor. Study participants will be contacted, as applicable, and be informed of changes to the study visit schedule.

Circumstances that may warrant termination or suspension include, but are not limited to:

- Determination of unexpected, significant, or unacceptable risk to participants.
- Demonstration of efficacy that would warrant stopping.
- Insufficient compliance with protocol requirements.
- Data that are not sufficiently complete and/or evaluable.
- Determination that the primary endpoint has been met.
- Determination of futility.

The study may resume once concerns about safety, protocol compliance, and data quality are addressed, and satisfy the sponsor, the IRB, and/or the Food and Drug Administration (FDA).

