## 1 PROTOCOL SUMMARY

### 1.1 Synopsis

**Title:**  $[^{11}\text{C}]\text{-}(R)$ -Rolipram to Measure cAMP Signaling Before and After Ketamine

**Study Description:** This study will test the effects of ketamine infusion on the cAMP system in human brain to determine if ketamine mediates its antidepressant effects at least in part due to modulation of cAMP signaling.

**Objectives:** Primary Objective: To determine if ketamine infusions in depression causes increases in cAMP signaling as measured by  $[^{11}\text{C}]\text{-}(R)$ -rolipram binding.

Secondary Objectives: To determine if increases in  $[^{11}\text{C}]\text{-}(R)$ -rolipram correlate with symptomatic improvement in major depressive symptoms.

**Endpoints:** Primary Endpoint: measurement of PDE4 density (volume of distribution  $V_T$ ) in brains of individuals with major depressive disorder (MDD) before and after administration of ketamine. Secondary Endpoints: Clinical rating scales of depression, including MADRS, HAM-D.

**Study Population:** 35 inpatient participants with major depressive disorder eligible for ketamine administration and enrolled in protocols 19-M-0107 “Ketamine and AMPA”, 17-M-0060 “Neuropharmacology of Ketamine” or 15-M-0188 “Neurobiology of Suicide.”. Participants may be male or female. They must be between 18 and 70 years old. MDD participants must be in good medical health and provide informed consent.

**Phase:** N/A

**Description of Sites/Facilities** Screening, PET imaging and ketamine infusion will be performed at the NIH Clinical Center.

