## 4 STUDY DESIGN

### 4.1 Overall Design

- **Site:** This single-site study will be conducted at the NIH Clinical Center.
- **Hypothesis:** We hypothesize that PDE4 levels as quantified by [C](R)-rolipram in the brains of subjects suffering from a major depressive episode will be increased with ketamine administration, and that these levels will correlate with clinical rating scales.
- **Type of Design:** MDD participants will be studied with [C](R)-rolipram prior to and after ketamine infusion.

- **Study Groups:** Individuals with MDD
- **Study intervention:** Two PET scans with [C](R)-rolipram and MRI of brain.
- **Interim Analysis:** None.
- **Stratifications:** None.

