### **6.3 Measures to Minimize Bias: Randomization and Blinding**

This study is neither randomized nor blinded.

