#### 9.3.2 Evaluable for objective response

Participants will be evaluated on the basis of completion of two PET scans as the primary endpoint. Ketamine infusion has been shown to exert an antidepressant effect, which will be evaluated based on changes in clinical rating scales from pre-ketamine baseline, which will then be correlated to change in PET scans.

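### Does the closure list in Section 10.2 contradict the statement in Section 4.1 that no interim analysis is planned?

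*Combined protocol and SAP*

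**What the plan says.** Section 4.1 (Overall Design) has an entry for "Interim Analysis" and answers it with None. Section 9 agrees: Sections 9.4.1 and 9.4.2 plan one paired t-test of V_T before and after ketamine, and nothing in Section 9 gives a look time, a boundary, an alpha or a futility criterion. Section 9.2 aims to scan 23 participants out of up to 35 recruited.

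Section 10.2 (Study Discontinuation and Closure) introduces its list with "Circumstances that may warrant termination or suspension include, but are not limited to". Besides risk, compliance and data quality, the list has three entries that sound statistical: "Demonstration of efficacy that would warrant stopping", "Determination that the primary endpoint has been met" and "Determination of futility".

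The primary endpoint is described in two ways. The synopsis has "Primary Endpoint: measurement of PDE4 density (volume of distribution" and continues with V_T before and after ketamine; Sections 3 and 9.1 agree. Section 9.3.2 speaks of "completion of two PET scans as the primary endpoint". Section 6.3 states: "This study is neither randomized nor blinded".

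**The concern.** If the primary endpoint is V_T, then judging that it has been met, or that efficacy is shown, seems to require looking at V_T while the study is running. Section 4.1 says no such look is planned. The study is open, so nothing hides the accumulating values, and Section 10.5 has a report on data and safety going to the safety monitor about once a year without saying whether V_T is in it.

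Stopping at the first significant t-test would inflate the type I error and push the estimated change upward. A futility stop would pull the estimate downward. Section 4.2 says the study is meant to inform a larger one, so the size of the V_T change is its main product. Early closure would also leave fewer pairs for the secondary correlation between V_T change and the rating scales.

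**Working it through.** **Setting the sections side by side**

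1. Section 4.1 answers the question directly and for this study: no interim analysis. Section 9 contains nothing to the contrary.
2. Section 10.2 says what may justify closure. It schedules no look, requires no test and gives no threshold.
3. The three entries fit this study poorly, as standard text does. Under Sections 4.1 and 6.1.1 the study intervention is two PET scans and an MRI, and the ketamine is given under other protocols (Sections 1.2 and 1.3), so efficacy of the intervention has no clear meaning. The sentence in Section 10.2 on resuming the study names only safety, compliance and data quality. Nearby text is equally unadapted: Section 10.7 speaks of each clinical site in a single-site study, and the abbreviations list ITT, ANCOVA, LSMEANS and DSMB, none of which Section 9 uses.
4. Harmless readings exist. With the wording of Section 9.3.2, the endpoint is met when the planned scan pairs are complete. Futility can mean that too few pairs can be obtained.

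The documents state no error rate or power, so there is no planned figure to reproduce. If Section 4.1 is followed there is one test at 23 pairs; at an assumed two-sided 0.05, simulation gives a type I error of 5.0% and an unbiased mean (6.00 for a true 6%, 12.00 for a true 12%).

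**What would happen if Section 4.1 were ignored**

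Inputs from the documents: 23 pairs; a 12% rise with P<0.001 in the earlier SSRI cohort of 23 (Section 9.2). Assumptions: two-sided 0.05 at each look; stop at the first significant result; looks at 12 and 23 pairs, or at 8, 15 and 23; normal changes; a true change of 12%, or half of it.

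SD of change, if the SSRI P value came from a two-sided paired t-test (the documents do not say):

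- SD = 12 × √23 / t(22). At P = 0.001, t = 3.792, so SD = 57.55 / 3.792 = 15.2%. This is the largest value compatible with P<0.001.
- A lower value for range, at P = 0.00001: 57.55 / 5.694 = 10.1%.

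Results over 400,000 simulated trials per cell:

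| | One test at 23 | Looks 12, 23 | Looks 8, 15, 23 |
|---|---|---|---|
| Type I error | 5.0% | 8.4% | 11.0% |
| Mean estimate, true 12%, SD 15.2% | 12.0% | 12.7% | 13.2% |
| Mean estimate, true 12%, SD 10.1% | 12.0% | 12.1% | 12.4% |
| Mean estimate, true 6%, SD 15.2% | 6.0% | 6.6% | 6.9% |
| Mean estimate, true 6%, SD 10.1% | 6.0% | 6.5% | 6.8% |
| Stopped early, true 12%, SD 15.2% | none | 70% | 83% |
| Stopped early, true 12%, SD 10.1% | none | 96% | 99% |

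The upward bias is 0.1 to 1.2 points.

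Precision, half-width = t(n−1) × SD / √n:

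- 23 pairs, SD 15.2%: 2.074 × 15.18 / 4.796 = 6.6 points (4.4 at SD 10.1%).
- 12 pairs, SD 15.2%: 2.201 × 15.18 / 3.464 = 9.6 points.
- 8 pairs, SD 15.2%: 2.365 × 15.18 / 2.828 = 12.7 points.

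Smallest correlation reaching 0.05, r = t / √(n − 2 + t²), with t on n − 2 degrees of freedom: 0.41 at 23 pairs, 0.58 at 12, 0.71 at 8.

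Futility only (stop at 12 pairs if t<1, SD 15.2%): type I error falls to 2.1%. Power falls from 44% to 40% at a true 6% and from 95% to 93% at a true 12%. A true 6% reads as 5.3%, a true 12% as 11.8%.

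**Would a formal boundary help?** Take one look at 12 pairs at p<0.001, then 0.05 at 23. Type I error is 5.1%. At SD 10.1% and a true 12%, however, 44% of trials stop at 12 pairs and the mean estimate is 12.4%, against 12.1% with the unadjusted look. At SD 15.2% the mean is 12.3%, against 12.7%. The boundary protects the error rate but not the estimate, which is what this study is for.

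**The case for a change.** The strongest case is that no sentence reconciles the two sections. The definitions in Sections 1.1, 3 and 9.1 make V_T the endpoint, so the natural reading of an endpoint being met is a result on V_T. The team can see the data, and a stopping policy cannot credibly be settled once V_T has been seen. Clarifying it would cost a few words. Although the mean bias is small, a stop at 12 or 8 pairs would cost real precision and much of the secondary analysis.

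The wording is indeed unreconciled, and a V_T-driven stop would do the harm described, more through lost pairs than through bias. What does not stand is the step from unreconciled wording to a defective plan. The objection needs a general list of possible reasons to override a specific design statement, and it needs looks that no section describes. Nor could such a stop pass unnoticed: Section 10.2 requires the investigator to inform participants, the IRB and the sponsor promptly of premature termination, and a reader would see fewer than 23 pairs analysed.

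**Conclusion.** No change is called for. The documents leave a small gap in wording that analysts fill sensibly: the specific statement in Section 4.1 governs, V_T is tested once, and the closure entries are read as completion or feasibility grounds. On that reading no planned result is wrong and the type I error stays at its nominal level.

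The size of the hypothetical harm is a type I error of about 8% or 11% in place of 5%, and an upward shift of 0.1 to 1.2 points in the mean estimate, against a half-width of 4.4 to 6.6 points at 23 pairs. A stop at 12 pairs would widen the interval to 9.6 points at the larger SD. All of this depends on assumed look times, a two-sided 0.05 and an SD back-calculated from one reported P value. A sentence ruling out V_T-based stopping would do no harm, but it would only repeat Section 4.1, and a formal interim boundary would bring no gain for the estimate. The conclusion would differ if any section scheduled a review of V_T for the purpose of closure; none does.

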### **10.3 Confidentiality and Privacy**

Participant confidentiality and privacy are strictly held in trust by the participating investigators, their staff, and the sponsor(s). This confidentiality is extended to cover testing of biological samples in addition to the clinical information relating to participants. Therefore, the study protocol, documentation, data, and all other information generated will be held in strict confidence.

All research activities will be conducted in as private a setting as possible.

The study monitor, other authorized representatives of the sponsor, representatives of the IRB, and/or regulatory agencies may inspect all documents and records required to be maintained by the investigator, including but not limited to medical records (office, clinic, or hospital) and pharmacy records for the participants in this study. The clinical study site will permit access to such records.

The study participant's contact information will be securely stored at the NIH for internal use during the study. At the end of the study, all records will continue to be kept in a secure location for as long a period as dictated by the reviewing IRB, institutional policies, or sponsor requirements.

To further protect the privacy of study participants, a Certificate of Confidentiality (COC) has been issued by the NIH. This certificate protects identifiable research information from forced disclosure. It allows the investigator and others who have access to research records to refuse to disclose identifying information on research participation in any civil, criminal, administrative, legislative, or other proceeding, whether at the federal, state, or local level. By protecting researchers and institutions from being compelled to disclose information that would identify research participants, COCs help achieve the research objectives and promote participation in studies by helping ensure confidentiality and privacy to participants.

See Section 10.4 for information regarding sharing of research data during or after completion of the study.

### **10.4 Future use of Stored Specimens and Data**

Genetic testing will not be performed in this protocol. No samples will be stored or shared.

In the consent form, we ask permission of the participant (yes/no response) to share imaging and other research data during or after completion of the study with collaborating laboratories at the NIH or outside of the NIH and/or submitted to open-access repositories for secondary research that may or may not involve a collaboration with the NIMH. Such open access repositories (e.g., OpenNeuro, sponsored by the NIMH) allows anyone to access the data for any purpose. Data will be stripped of all identifiers, including name, address, contact information, and medical record number prior to sharing. In addition, the face will be removed from MRI images. The data may be coded, but the key to the code will not be provided to any collaborator or party external to the NIH. After the study is completed, the de-identified data and

the code may be indefinitely maintained at the NIH and used for secondary analyses. In contrast to data, no biological samples will be shared.

## **10.5 Safety Oversight**

Monitoring for this study will be performed by the independent safety monitor (ISM), [name], who is a board-certified psychiatrist with full clinical privileges at the NIH Clinical Center.

The PI will prepare a report on data and safety parameters for the ISM approximately every 12 months. The ISM will provide a written monitoring report to be submitted to the IRB at the time of continuing review.

## **10.6 Clinical Monitoring**

Clinical site monitoring is conducted to ensure that the rights and well-being of trial participants are protected, that the reported trial data are accurate, complete, and verifiable, and that the conduct of the trial complies with the currently approved protocol/amendment(s), with International Conference on Harmonization Good Clinical Practice (ICH GCP), and with applicable regulatory requirement(s).

As per ICH-GCP 5.18 and FDA 21 CFR 312.50 clinical protocols are required to be adequately monitored. Monitoring for the NIH site will be conducted according to the "NIMH Intramural Program Guidelines for Monitoring of Clinical Trials". Monitors under contract to the NIMH OCD ORO will visit the NIH site to monitor aspects of the study in accordance with the appropriate regulations and the approved protocol. The objectives of a monitoring visit will be: 1) to verify the existence of signed informed consent documents and documentation of the ICF process for each monitored subject; 2) to verify the prompt and accurate recording of all monitored data points, and prompt reporting of all SAEs; 3) to compare abstracted information from clinical databases (e.g. CTDB) with individual subjects' records and source documents (subjects' charts, laboratory analyses and test results, physicians' progress notes, nurses' notes, and any other relevant original subject information); and 4) to help ensure investigators are in compliance with the protocol. The monitors also will inspect the clinical site regulatory files to ensure that regulatory requirements (Office for Human Research Protections-OHRP), FDA, and applicable guidelines (ICH-GCP) are being followed. During the monitoring visits, the investigator (and/or designee) and other study personnel will be available to discuss the study progress and monitoring visit.

The investigator (and/or designee) will make study documents (e.g., consent forms, clinical database records and pertinent hospital/sources or clinical records readily available for inspection by the local IRB, FDA, the site monitors, and the NIMH staff for confirmation of the study data.

A specific protocol monitoring plan will be discussed with the Principal Investigator and study staff. The plan will outline the frequency of monitoring visits based on such factors as study enrollment, data collection status and regulatory obligations.

## **10.7 Quality Assurance and Quality Control**

Each clinical site will perform internal quality management of study conduct, data and biological specimen collection, documentation and completion.

Following written Standard Operating Procedures (SOPs), the monitors will verify that the clinical trial is conducted, and data are generated and biological specimens are collected, documented (recorded), and reported in compliance with the protocol, International Conference on Harmonization Good Clinical Practice (ICH GCP), and applicable regulatory requirements (e.g., Good Laboratory Practices (GLP), Good Manufacturing Practices (GMP)).

The investigational site will provide direct access to all trial related sites, source data/documents, and reports for the purpose of monitoring and auditing by the sponsor, and inspection by local and regulatory authorities.

## **10.8 Data Handling and Record Keeping**

### **10.8.1 Data Collection and Management Responsibilities**

Data collection is the responsibility of the clinical trial staff at the site under the supervision of the PI. The PI is responsible for ensuring the accuracy, completeness, legibility, and timeliness of the data reported.

All source documents will be completed in a neat, legible manner to ensure accurate interpretation of data. Hardcopies of the study visit worksheets will be provided for use as source document worksheets for recording data for each participant enrolled in the study. Data recorded in the electronic case report form (eCRF) derived from source documents will be consistent with the data recorded on the source documents.

Clinical data (including AEs, eligibility, and primary outcome data) will be entered into the Clinical Trials Database (CTDB) at NIH. CTDB complies with the Federal Information Security Management Act of 2002 and 21 CFR Part 11. The data system includes audit trail, password protection, and control staff access level to the application and data. Edit checks implemented at the eCRF include: data type validation and numeric range checks. Clinical data will be entered directly from the source documents.

### **10.8.2 Study Records Retention**

Study documents should be retained for a minimum of 2 years after the last approval of a marketing application in an International Conference on Harmonisation (ICH) region and until there are no pending or contemplated marketing applications in an ICH region or until at least 2 years have elapsed since the formal discontinuation of clinical development of the study intervention, and as per the NIH Intramural Records Retention Schedule. No records will be destroyed without the written consent of the sponsor, if applicable. It is the responsibility of the sponsor to inform the investigator when these documents no longer need to be retained.

